**Table 10-2 Base Renal Monitoring**

Assessments	Assessment Frequency
Serum creatinine, Electrolytes (Na, Ca, K)	1. Single baseline
Urine Dipstick* (Spot urine sample)	2. Steady State assessment
	3. 6-monthly during study
	4. Final visit ≥ 48h after last dose

\*For point of care tests (POCT), the clinical sites in China will be allowed to analyze these tests as per clinical site practice (refer to China laboratory manual for further details)

Every renal laboratory trigger or renal event as defined in Table 16-6 should be followed up by the investigator or designated personnel at the trial site as summarized in Table 16.7.

## 10.3 Committees

### 10.3.1 Data Monitoring Committee

This study will include a data monitoring committee (DMC) which will function independently of all other individuals associated with the conduct of this clinical trial, including the site investigators participating in the study. The DMC will evaluate the results of the futility analysis.

Specific details regarding composition, responsibilities, data monitoring, and meeting frequency, and documentation of DMC reports, minutes, and recommendations will be described in a separate charter that is established between the sponsor and the DMC.

### 10.3.2 Steering Committee

The Steering Committee (SC) consists of a limited number of investigators drawn from the pool of investigators participating in the trial, i.e., not being members of the DMC, AC or Novartis representatives from the Clinical Trial Team.

The SC will help to conduct the study with highest scientific and ethical standards by providing input to the study protocol and/or potential amendments as required. Together with the clinical trial team, the SC will also develop recommendations for publications of study results including authorship rules. The details of the role of the steering committee will be defined in the steering committee charter.

### **10.3.3 Adjudication committee**

To enhance the safety assessment, more specifically relative to 1) anaphylactic events, 2) neoplastic events, and 3) major cardio-cerebrovascular events, 3 ACs, independent panels of experts external to Novartis, will provide reviews of identified potential events in a blinded manner.

All the details of the adjudication processes including the committee members are included in the AC charters.

## **11 Data Collection and Database management**

### **11.1 Data collection**

Designated investigator staff will enter the data required by the protocol into the Electronic Case Report Forms (eCRF). The eCRFs have been built using fully validated secure web-enabled software that conforms to 21 CFR Part 11 requirements, Investigator site staff will not be given access to the EDC system until they have been trained. Automatic validation programs check for data discrepancies in the eCRFs, allow modification and/or verification of the entered data by the investigator staff.

The investigator/designee is responsible for assuring that the data (recorded on eCRFs) (entered into eCRF) is complete, accurate, and that entry and updates are performed in a timely manner. The Investigator must certify that the data entered are complete and accurate.

After final database lock, the investigator will receive copies of the participant data for archiving at the investigational site.

All data should be recorded, handled, and stored in a way that allows its accurate reporting, interpretation, and verification.

### **11.2 Database management and quality control**

Novartis personnel (or designated CRO) will review the data entered by investigational staff for completeness and accuracy. Electronic data queries stating the nature of the problem and requesting clarification will be created for discrepancies and missing values and sent to the investigational site via the EDC system. Designated investigator site staff are required to respond promptly to queries and to make any necessary changes to the data.

Concomitant treatments and prior medications entered into the database will be coded using the World Health Organization (WHO) Drug Reference List, which employs the Anatomical Therapeutic Chemical classification system. Medical history/current medical conditions and AEs will be coded using the MedDRA terminology.

Laboratory samples will be processed centrally and the results will be sent electronically to Novartis. Stool samples will be processed by local labs and the results will be captured by Novartis via eCRFs.

ECG readings will be processed centrally and results will be sent electronically to Novartis.

[REDACTED] The remaining PROs will be completed by participants on site on the day of applicable visits. [REDACTED]

[REDACTED] The source data collected by the vendor will be sent electronically to Novartis.

At selected sites digital photos will be taken as per [Section 8.5.5](#). These photographs will be sent electronically by the site to the central dermatology-imaging vendor and from there electronically to Novartis.

Dates of screenings, randomizations and screen failures, as well as randomization codes and data about all study treatment (s) dispensed to the participant and all dosage changes will be tracked using IRT. The system will be supplied by a vendor, who will also manage the database. The data will be sent electronically to Novartis (or a designated CRO) at specific timelines.

Each occurrence of a code break via IRT will be reported to the clinical team and monitor. The code break functionality will remain available until study shut down or upon request of Novartis.

Once all the necessary actions have been completed and the database has been declared to be complete and accurate, it will be locked and the treatment codes will be unblinded and made available for data analysis/moved to restricted area to be accessed by independent programmer and statistician. Any changes to the database after that time can only be made after written agreement by Novartis development management.

### **11.3 Site monitoring**

Before study initiation, at a site initiation visit or at an investigator's meeting, a Novartis/delegated CRO representative will review the protocol and data capture requirements (i.e. eCRFs) with the investigators and their staff. During the study, Novartis employs several methods of ensuring protocol and GCP compliance and the quality/integrity of the sites' data. The field monitor will visit the site to check the completeness of participant records, the accuracy of data capture / data entry, the adherence to the protocol and to Good Clinical Practice, the progress of enrollment, and to ensure that study treatment is being stored, dispensed, and accounted for according to specifications. Key study personnel must be available to assist the field monitor during these visits. Continuous remote monitoring of each site's data may be performed by a centralized Novartis/delegated CRO/CRA organization. Additionally, a central analytics organization may analyze data & identify risks & trends for site operational parameters, and provide reports to Novartis clinical teams to assist with trial oversight.

The investigator must maintain source documents for each participant in the study, consisting of case and visit notes (hospital or clinic medical records) containing demographic and medical information, laboratory data, electrocardiograms, and the results of any other tests or assessments. All information on eCRFs must be traceable to these source documents in the participant's file. Data not requiring a separate written record will be defined before the study start and will be recorded directly on the CRFs. The investigator must also keep the original informed consent form signed by the participant (a signed copy is given to the participant).

The investigator must give the monitor access to all relevant source documents to confirm their consistency with the data capture and/or data entry. Novartis monitoring standards require full verification for the presence of informed consent, adherence to the inclusion/exclusion criteria,

documentation of SAEs, and of data that will be used for all primary variables. Additional checks of the consistency of the source data with the eCRFs are performed according to the study-specific monitoring plan. No information in source documents about the identity of the participants will be disclosed.

## **12 Data analysis and statistical methods**

Any data analysis carried out independently by the investigator should be submitted to Novartis before publication or presentation.

Inferential efficacy comparisons with placebo will be focus on the placebo-controlled period (i.e. up to Week 12).

Data analyses will be presented by treatment group. For symptomatic dermographism and cold urticaria, efficacy and safety data for the placebo-controlled period will be presented by the 3 treatment groups of ligelizumab 120 mg q4w, ligelizumab 72 mg q4w, and placebo. For cholinergic urticaria, efficacy and safety data for the placebo-controlled period will be presented by the 2 treatment groups of ligelizumab 120 mg q4w and placebo.

These treatment groups represent the treatment participants will be assigned to during the placebo-controlled period.

For the entire treatment period or study period, data will be presented by a combination of the "original" and "after switch" treatment groups (e.g. placebo - ligelizumab 120 mg q4w), as appropriate.

### **12.1 Analysis sets**

For each CINDU cohort, the following analysis sets will be used in this trial:

The Randomized Analysis Set (RAS) consists of all randomized participants, regardless of whether or not they receive a dose of study drug. Participants will be analyzed according to the treatment they are assigned.

The Full Analysis Set (FAS) comprises all participants to whom study treatment has been assigned and who received at least one dose of study treatment. Participants will be analyzed according to the treatment they have been assigned to.

The Safety Set (SAF) includes all participants who received any study treatment. Participants will be analyzed according to the study treatment(s) received. The actual treatment will be defined as the treatment received over the study. In case of error in dispensation, the actual treatment will correspond to the treatment which was given most often.

### **12.2 Participant demographics and other baseline characteristics**

For each CINDU cohort, demographic and other baseline data including disease characteristics will be listed and summarized descriptively by treatment group for the Safety set.

Categorical data will be presented as frequencies and percentages. For continuous data, mean, standard deviation, median, minimum, and maximum will be presented. For selected parameters, 25th and 75th percentiles will also be presented.

Relevant medical histories and current medical conditions at baseline will be coded using the MedDRA dictionary. They will be summarized by system organ class and preferred term of the MedDRA dictionary, by treatment group.

Summaries for cardiovascular and urticaria specific medical history will also be provided.

## 12.3 Treatments

For each CINDU cohort, the Safety set will be used for the analyses below. Categorical data will be summarized as frequencies and percentages. For continuous data, mean, standard deviation, median, 25th and 75th percentiles, minimum, and maximum will be presented.

Number of participants and the duration of exposure (in weeks) to each treatment and dose will be summarized by means of descriptive statistics using the safety set. In addition, the number of doses, total cumulative dose, and number of missed doses will be presented.

Prior medications are defined as medications taken and stopped prior to first dose of study treatment. Prior medications will be summarized based on Safety set. Prior medications for CINDU will be summarized by type of therapy, preferred term and treatment group. Prior medications non-related to CINDU will be summarized by Anatomical Therapeutic Chemical (ATC) code and preferred term.

Concomitant medications prior to and after the start of the study treatment will be summarized by treatment for the safety set separated for urticaria related background medications and non-CINDU related medications. CINDU related background medications will be summarized by type of therapy, preferred term and treatment group. Non-CINDU related concomitant medications will be summarized by preferred term.

## 12.4 Analysis of the primary endpoint(s)/estimand(s)

This section will detail the statistical analysis of the primary estimand. Details of the hypothesis testing strategy including primary and secondary endpoints to handle multiplicity are provided in [Section 12.5](#).

### 12.4.1 Definition of primary endpoint(s)/estimand(s)

The primary estimand for the three CINDU cohorts are provided in [Section 2.1](#).

### 12.4.2 Statistical model, hypothesis, and method of analysis

#### Symptomatic Dermographism:

The aim is to estimate the treatment effect of ligelizumab compared to placebo, for the target population on the primary endpoint (i.e. change from baseline to week 12 in Total Fric Score). The justification of the corresponding primary estimand is detailed in [Section 2.1](#).

The primary analysis method is based on a two-sample t-test.

The null hypothesis test ( $H_0$ ) for the primary endpoint is that the change from baseline at Week 12 in Total Fric Score in any of the ligelizumab groups (low or high dose) is not superior to the placebo group:

$$H_{01.SDerm}: \mu_{\text{ligelizumab}} \geq \mu_{\text{Placebo}} \text{ versus } H_{A1.SDerm}: \mu_{\text{ligelizumab}} < \mu_{\text{Placebo}}$$

where  $\mu$  is the mean change from baseline of Total Fric Score at week 12, negative value indicates improvement.

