- **Treatment of interest:** ligelizumab or the placebo treatment (no further treatment for patients who discontinue treatment due to AE, lack of efficacy or intake of prohibited medications) with stable H1-antihistamines at local-approved doses as background medication + allowed rescue medication. The dose of the allowed background medication for CINDU must remain stable during the trial. Further details about the investigational treatment and control treatment are provided in [Section 6](#).
- **Handling of remaining intercurrent events:**
  1. Discontinuation of initial assigned study treatment prior to Week 12 due to adverse events (AE), use of prohibited medications or lack of efficacy (LoE): Participants who discontinue from study treatment early will be encouraged to stay in the study as detailed in [Section 9.1.1](#). Retrieved drop out (RDO) data collected after study treatment discontinuation will be used for analysis (treatment policy).
  2. Discontinuation of initial assigned study treatment prior to Week 12 due to reasons other than adverse events (AE), use of prohibited medications, or lack of efficacy

- (LoE): had participants taken the assigned treatment up to Week 12 (hypothetical strategy).
3. Use of prohibited medications prior to Week 12 and not result in treatment discontinuation: ignore (treatment policy).
  4. Missed treatment prior to Week 12 due to other non-human controlled emergency situations (e.g. COVID-19): had participants not missed treatment prior to Week 12 (hypothetical strategy).
- **The summary measure:**
    1. Symptomatic Dermographism: difference in mean change from baseline in Total Fric Score at Week 12 between treatments (ligelizumab 72 mg q4w vs placebo and ligelizumab 120 mg q4w vs placebo)
    2. Cold urticaria: difference in mean change from baseline of CTT at Week 12 between treatments (ligelizumab 72 mg q4w vs placebo and ligelizumab 120 mg q4w vs placebo)
    3. Cholinergic urticaria: difference in mean change from baseline in itch NRS in response to the pulse-controlled ergometry test at Week 12 between treatments (ligelizumab 120 mg q4w vs placebo)

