### **6.4.2 Treatment assignment, randomization**

At Week 0 (Day 1/Visit 100), all eligible participants in the symptomatic dermatographism and cold urticaria cohorts will be randomized into 4 arms via IRT in a 2:2:1:1 ratio to ligelizumab 120 mg, ligelizumab 72 mg, placebo to ligelizumab 120 mg or placebo to ligelizumab 72 mg while all eligible participants in the cholinergic urticaria cohort will be randomized in a 1:1 ratio to ligelizumab 120 mg or placebo to ligelizumab 120 mg. The investigator or his/her delegate will contact the IRT system after confirming that the participant fulfills all the inclusion/exclusion criteria. The IRT call must be made only after provocation test results are available.

The IRT system will assign a randomization number to the participant, which will be used to link the participant to a treatment arm and will specify a unique medication number for the package of study drug treatment to be dispensed to the participant. This information will not be provided to the blinded site user. Only the unblinded pharmacist or delegate can access the participant treatment details and is provided with the kit details. All kits of study treatment assigned by the IRT will be recorded in the IRT system.

The randomization numbers will be generated using the following procedure to ensure that treatment assignment is unbiased and concealed from participants and investigator staff. A participant randomization list will be produced by the IRT provider using a validated system that automates the random assignment of participant numbers to randomization numbers. These randomization numbers are linked to the different treatment arms, which in turn are linked to medication numbers. A separate medication list will be produced by Novartis Global Clinical Supply (GCS) using a validated system that automates the random assignment of medication numbers to packs containing the study treatment.

Since both adults and adolescent participants will be enrolled into this study, randomization will be stratified by age group (adolescent 12-17 years old and adult  $\geq 18$  years old). In addition, randomization for adults will be stratified by region to ensure a balanced assignment to each treatment group.

The randomization scheme for participants will be reviewed and approved by a member of the Randomization Office.

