#### 12.4.5 Sensitivity analyses for primary endpoint/estimand

For all three CINDU cohorts, the following sensitivity analysis will be performed for the primary estimand, to assess the robustness of the estimation in the presence of deviations from the assumptions specified in the primary analysis.

- The ANCOVA (Analysis of covariance) model with treatment group, baseline scores, region/country as covariates will be performed. Intercurrent events will be handled in the same way as in the primary analysis.
- To account for uncertainty in the imputations, the tipping point analyses will be considered, if needed.

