## 12.8.1 Primary endpoint(s)

### Symptomatic Dermographism

Since two ligelizumab dose regimens will be tested versus placebo with respect to the primary endpoints (change from baseline in Total Fric Score at Week 12), the type-I-error will be split to 1.25% one-sided for each comparison.

Assuming the treatment difference in change from baseline to Week 12 in Total Fric Score is at least 1.3 in favor of the ligelizumab group, and a standard deviation of approximately 1.7, a sample size of approximate 56 participants per group and a drop-out rate of 10% provides 93.7% power to show that the primary analysis based on a two-sample t-test will be statistically significant at the one-sided 1.25% significance level (SAS 9.4, PROC POWER, difference in two sample means).

Mean changes from baseline in Total Fric Score of -0.6 (standard deviation: 1.4) in placebo group, -1.78 (standard deviation: 1.66) in omalizumab 150 mg group, and - 2.0 (standard deviation: 1.67) in omalizumab 300 mg group have been reported in [Maurer et al 2017](#).

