### Cholinergic Urticaria

Assuming the treatment difference in change from baseline to Week 12 in itch NRS following the pulse-controlled ergometry test is at least 1.65 in favor of the ligelizumab 120 mg q4w group, and a standard deviation of approximately 3.0, a sample size of approximate 79 participants per group and a drop-out rate of 10% provides 90.2% power to show that the primary analysis based on a two-sample t-test will be statistically significant at the one-sided 2.5% significance level (SAS 9.4, PROC POWER, difference in two sample means).

Median pre-treatment itch VAS of 60 (25th percentile=40, 75th percentile=80) and median post-treatment itch VAS of 30 (25th percentile=20, 75th percentile=70) in the overall population after 4 doses of omalizumab 300 mg have been reported in [Gastaminza et al](#).

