5.1 Classification of study regions by country

Table 5-1 Region stratification defined by country enrollment:

Name	Study Countries
Asia	China; Korea; Malaysia; Thailand; Singapore; Vietnam; Philippines; Taiwan
Non-Asia	Other

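### The planned primary t-test on change uses neither the baseline score nor the randomization strata; ranking a pairwise ANCOVA as primary is an optional, low-cost gain in precision whose size the documents cannot fix.

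*Protocol*

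**What the plan says.** Protocol 12.4.2 gives one sentence for each cohort: "The primary analysis method is based on a two-sample t-test". SAP 2.5.2 repeats it. The variable is change from baseline to Week 12 in Total Fric Score (TFS), critical temperature threshold or itch NRS. For cholinergic urticaria the summary measure in protocol 2.1 is the "difference in mean change from baseline in itch NRS in response to the pulse-controlled ergometry test at Week 12 between treatments"; the other two cohorts have the same form.

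Protocol 6.4.2 stratifies randomization by age group (adolescent, adult) and adds that "randomization for adults will be stratified by region to ensure a balanced assignment to each treatment group". SAP 5.1, under "Region stratification defined by country enrollment", defines two regions, Asia and Non-Asia.

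Baseline adjustment appears in protocol 12.4.5, as a sensitivity analysis: "The ANCOVA (Analysis of covariance) model with treatment group, baseline scores, region/country as covariates will be performed". Age group is not in that model. The itch NRS change endpoint in protocol 12.5 is also tested by a two-sample t-test.

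After early termination, the SAP (sections 1, 2.5.2, 2.5.4 and 4) cancels the primary tests and the sensitivity analyses.

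**The concern.** A t-test on change is an ANCOVA with the baseline slope fixed at 1 and no other covariates. If the true slope is below 1, the change score carries baseline noise that a fitted slope would remove. If a stratum is prognostic, stratified allocation balances it between arms, but the t-test leaves its variance in the error term. In both cases the trial pays for information it already collects and does not use it in the primary test. At stake is some power, most of all in cholinergic urticaria, which has the lowest planned primary power of the three.

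**Working it through.** **Inputs (protocol 12.8.1).** Completers per arm after 10% drop-out: 79 × 0.9 → 71; 56 × 0.9 → 50; 34 × 0.9 → 30. Effect / SD of change: 1.65 / 3.0, 1.3 / 1.7, 10 °C / 8 °C. One-sided alpha: 2.5%, 1.25%, 1.25%.

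**Step 1: the plan's own figures.** Noncentral t with 2n − 2 df and noncentrality d / (SD × √(2/n)) = 3.28, 3.82, 4.84:

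- cholinergic 90.2% (plan: "a standard deviation of approximately 3.0, a sample size of approximate 79 participants per group and a drop-out rate of 10% provides 90.2% power");
- dermographism 93.7% (plan: "a standard deviation of approximately 1.7, a sample size of approximate 56 participants per group and a drop-out rate of 10% provides 93.7% power");
- cold urticaria 99.4% (plan: above 99%).

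All three reproduce.

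**Step 2: ANCOVA power.** Let s0 and s1 be the baseline and Week 12 SDs, c the SD of change and r the baseline–Week 12 correlation. Then r = (s0² + s1² − c²) / (2·s0·s1), the slope is r·s1/s0, and the residual variance relative to the t-test is V = s1²(1 − r²)/c². I charge three covariates (baseline and two stratum terms, the latter taken as non-prognostic): df = 2n − 5, and variance inflated by 1 + 3/(2n − 6) for chance imbalance.

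**Step 3: cholinergic urticaria.** The only pre/post spread given for a primary endpoint is a cited omalizumab study: "Median pre-treatment itch VAS of 60 (25th percentile=40, 75th percentile=80) and median post-treatment itch VAS of 30 (25th percentile=20, 75th percentile=70". As a normal proxy on a 0–10 scale, SD = IQR/1.349/10: s0 = 40/13.49 = 2.97, s1 = 50/13.49 = 3.71. With c = 3.0, r = (8.79 + 13.73 − 9)/21.98 = 0.62, slope 0.77, V = 0.95.

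| s0 | s1 | r | V | t-test | ANCOVA |
|---|---|---|---|---|---|
| 2.97 | 3.71 | 0.62 | 0.95 | 90.2% | 91.1% |
| 2.97 | 3.00 | 0.49 | 0.76 | 90.2% | 95.9% |
| 2.50 | 3.71 | 0.59 | 0.99 | 90.2% | 89.9% |
| any, slope 1 | | | 1 | 90.2% | 89.6% |

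A simulation of the first row (20,000 trials, baseline as the only covariate) gave mean estimates of −1.644 (t-test) and −1.646 (ANCOVA) against a true −1.65, with power 90.4% and 91.6%. Both methods estimate the same quantity.

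If the same quartiles hold but c is 3.5 (an assumed value; protocol Table 12-3 stops at 3.0), power goes from 79.7% to 83.8%.

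**Step 4: dermographism.** No baseline SD or correlation is given. Entry needs a positive test (protocol 5.1), so baseline TFS lies in 1–4 (8.3.1.1) and its SD cannot exceed 1.5. If baseline is spread evenly (assumed), s0 = √1.25 = 1.12. With c = 1.7:

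| r | s1 | V | ANCOVA (t-test 93.7%) |
|---|---|---|---|
| 0.1 | 1.40 | 0.67 | 98.9% |
| 0.3 | 1.66 | 0.87 | 96.0% |
| 0.4 | 1.80 | 0.95 | 94.3% |
| 0.5 | 1.96 | 0.99 | 93.1% |

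At r = 0.6, s1 would be 2.12, above the maximum of 2.0 on a 0–4 scale. If the covariates explain nothing, power is 93.0%. With s0 = s1 = 1.44 and r = 0.3 it is 99.1%. The t-test leaves 100 − 93.7 = 6.3 points to gain.

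**Step 5: cold urticaria.** At 10 °C / 8 °C only 100 − 99.4 = 0.6 point is left to gain. If the covariates explain nothing, power is 99.1%.

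**Step 6: smaller effects.** A simulation used the SDs of change cited in 12.8.1 for cold urticaria (placebo 3.9; active 7.6 and 9.4), 30 per arm and, as assumptions, baseline SD 5 and an effect of 5 °C. At slope 1, going from t-test to pairwise ANCOVA lowers power from 81.3% to 79.5% (active SD 7.6) and from 65.2% to 62.8% (active SD 9.4). At slope 0.7, with active SD 7.6, it rises from 81.5% to 82.3%.

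**The case against.** The strongest reply is that nothing is broken. The t-test directly estimates the summary measure, matches the method used for sample size and reaches its stated power. The ANCOVA is already in the protocol, and only its rank and the age term are at issue. The sign of the benefit turns on an unknown slope. The cholinergic proxy is weak: post-treatment quartiles of 20 and 70 around a median of 30 are clearly skewed, and they come from a small study after active treatment. The calculation also assumes one common slope, although response rates of 38–44% at the scale floor are planned on active drug for TFS and itch NRS. All of this stands. It makes the change optional and rules out a single headline figure.

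A reader might infer three stronger things that the documents do not support:

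- **That omitting the strata makes the test invalid.** It does not. In a cholinergic simulation under the null with non-prognostic strata, the t-test rejected in 2.52% of trials and the ANCOVA in 2.48%, against a nominal 2.5%. Nothing in the documents shows that age group or region is prognostic.
- **That a gain near 8 points is to be expected in cholinergic urticaria.** This needs equal SDs and r = 0.3, so SDs of 3.0/√1.4 = 2.54 at both times. The cited quartiles widen after treatment.
- **That a result of this trial is affected.** At termination 39 participants were enrolled and 3 had completed Week 12 (SAP 1.1 and 1.1.2), and no test is run.

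**Conclusion.** The point holds as an optional precision improvement to the protocol's planned analysis, not as an error. At the planned effects, with three covariates charged:

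- **Cholinergic urticaria:** about 1 point of power if the cited quartiles are an acceptable proxy; otherwise from no gain or a slight loss to about 6 points.
- **Dermographism:** from a loss of about 1 point to a gain of about 6.
- **Cold urticaria:** a gain of at most 0.6 point, or a loss of about 0.3.

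If the slope is near 1 and the strata are not prognostic, ANCOVA costs about 1 point or less at the planned effects, and up to 2.4 points in the 5 °C check. The ranges rest on baseline and Week 12 SDs and correlations that I assumed or took from the cited quartiles. A prognostic stratum would add to the gain.

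**What to change.** In protocol 12.4.2, for each ligelizumab dose versus placebo, make the primary analysis an ANCOVA of change from baseline with treatment, baseline score and randomization stratum (adolescent; adult Asia; adult Non-Asia). Fit it in each imputed dataset on the two arms compared, and combine by Rubin's rules. If either arm has no adolescents, use region alone and place adolescents by country; protocol section 5 sets no minimum number of adolescents, so this can happen.

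Pairwise fitting matters because the cited cold urticaria SDs differ by arm. The pooled variance is (3.9² + 7.6²)/2 = 36.5 and (3.9² + 9.4²)/2 = 51.8 for the two pairs, but 53.8 for three arms jointly, which is 47% above the first pair.

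Move the t-test to 12.4.5 as sensitivity, and use the same ANCOVA for the itch NRS change endpoint in 12.5. Change SAP 2.5.2 only if inferential testing is ever run.

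The cost is wording in three protocol sections, up to three model degrees of freedom per comparison, and the possible small loss given above. In a live trial it would also need an approved amendment under protocol 14.1. The sample size does not change.
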